### ***Device Deficiencies***

A device deficiency may or may not be associated with subject harm (i.e., ADE or SADE); however, not all ADEs or SADEs are due to a device deficiency. The investigator should determine the applicable category for the identified or suspect device deficiency and report any patient harm separately. [REDACTED]

## **11.2 Monitoring for Adverse Events**

At each visit, after the subject has had the opportunity to spontaneously mention any problems, the investigator should inquire about AEs by asking the standard questions shown below and report as applicable:

- “Have you had any health problems since your last study visit?”
- “Have there been any changes in the medicines you take because of a new health issue since your last study visit?”

In addition, changes in any protocol-specific parameters and/or questionnaires evaluated during the study are to be reviewed by the investigator. Any untoward (unfavorable and unintended) change in a protocol-specific parameter or questionnaire response that is clinically relevant, in the opinion of the investigator, is to be reported as an AE. These clinically relevant changes will be reported regardless of causality.

## **11.3 Procedures for Recording and Reporting**

AEs are collected from the time of informed consent. Any preexisting medical conditions or signs/symptoms present in a subject prior to the start of the study (i.e., before informed consent

is signed) are not considered AEs in the study and should be recorded in the medical history section of the eCRF.

For each recorded event, the ADEs and SAEs documentation must include: date of occurrence, severity, treatment (if applicable), outcome, and assessments of the seriousness and causality. In addition, the investigator must document all device deficiencies reported or observed with the test product on the device deficiency eCRF. The site must submit all available information on ADEs, SAEs, and device deficiencies to the study sponsor immediately as follows:

- ADEs or SAEs are documented on the Serious Adverse Event and Adverse Device Effect eCRF within 24 hours of the investigator's or site's awareness.
- Device deficiencies are documented on the Device Deficiency eCRF within 24 hours of the investigator's or site's awareness.
- Additional relevant information after initial reporting must be entered into the eCRF as soon as the data become available.
- Document any changes to concomitant medications on the appropriate eCRFs.
- Document all relevant information from discharge summary, autopsy report, certificate of death etc., if applicable, in the narrative section of the Serious Adverse Event and Adverse Device Effect eCRF.

Note: Should the EDC system become nonoperational, the site must complete the appropriate paper serious adverse event and adverse device effect and/or device deficiency form. The completed form is emailed to the study sponsor at [[contact]](mailto:[contact]) for USA-based sites and at [[contact]](mailto:[contact]) for AUS-based sites, according to the timelines outlined above; however, the reported information must be entered into the EDC system once it becomes operational.

In addition to recording all AEs into the EDC system, any AEs and device deficiencies for non-study marketed devices/products (e.g., Alcon's or other manufacturers' products used concomitantly during the study will be considered and processed as spontaneous following the post market vigilance procedures) and should be communicated to the device's/product's manufacturer as per local requirements.

**Study sponsor representatives may be contacted for any protocol related question and their contact information is provided in the MOP that accompanies this protocol.**

Further, depending upon the nature of the AE or device deficiency being reported, the study sponsor may request copies of applicable portions of the subject's medical records. The

investigator must also report all AEs and device deficiencies that could have led to a SADE according to the requirements of regulatory authorities or the IRB/IEC.

### **Intensity and Causality Assessments**

Where appropriate, the investigator must assess the intensity (severity) of the AE based on medical judgment with consideration of any subjective symptom(s), as defined below:

#### ***Intensity (Severity)***

Mild	An AE is mild if the subject is aware of but can easily tolerate the sign or symptom.
Moderate	An AE is moderate if the sign or symptom results in discomfort significant enough to cause interference with the subject's usual activities.
Severe	An AE is severe if the sign or symptom is incapacitating and results in the subject's inability to work or engage in their usual activities.

For every AE in the study, the investigator must assess the causality (related or not related to the medical device or study procedure). An assessment of causality will also be performed by study sponsor utilizing the same definitions, as shown below:

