## 1 GLOSSARY OF TERMS

Names of Test Product(s)	Throughout this document, test product(s) will be referred to as the UNITY Vitreoretinal Cataract System (VCS).
Name of Comparator Product(s)	N/A
Adverse Device Effect (ADE)	
Adverse event related to the use of an investigational medical device or comparator.
 
Note: This definition includes adverse events resulting from insufficient or inadequate instructions for use, deployment, implantation, installation, or operation; any malfunction; and use error or intentional misuse.

Adverse Event (AE)	
Untoward medical occurrence, unintended disease or injury, or untoward clinical signs (including abnormal laboratory findings) in subjects, users or other persons, whether or not related to the investigational medical device or comparator and whether anticipated or unanticipated.
 
Note: For subjects, this definition includes events related to the investigational medical device, comparator, or the procedures involved. For users or other persons, this definition is restricted to the use of the investigational medical device or comparator.
 
Requirements for reporting adverse events in the study can be found in Section 11.

Anticipated Serious Adverse Device Effect (ASADE)	An effect which by its nature, incidence, severity, or outcome has been identified in the risk assessment.
Clinical Investigation Plan (CIP)	The document(s) stating the rationale, objectives, design, and prespecified analysis, methodology, organization, monitoring, conduct, and record-keeping of the clinical

	
investigation.
 
Note: The protocol and other documents referenced in the protocol (for example, the statistical analysis plan, the manual of procedures, the deviations and evaluability plan, and the protocol monitoring plan) comprise the CIP.

Clinical Investigation Report (CIR)/Clinical Study Report	
The document describing the design, execution, statistical analysis, and results of a clinical investigation. The clinical investigation report is synonymous with the clinical study report.

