## 6.4 Safety Objective(s)

Table 6-2

Safety Objective(s)

Objective(s)	Endpoint(s)
To obtain device-specific safety clinical data	

• Ocular and nonocular AEs and SAEs

• Device deficiencies

• Secondary surgical interventions

• Unplanned intraoperative procedures

[figure not shown]

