**Figure 11-1**

**Categorization of All Adverse Events**

\*In this study, only AEs related to the IP/device (i.e., UNITY VCS) are considered as device related ADE.

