#### ***Causality***

Related	An AE classified as related may be either definitely related or possibly related where a direct cause and effect relationship with the medical device or study procedure has not been demonstrated, but there is a reasonable possibility that the AE was caused by the medical device or study procedure.
Not Related	An AE classified as not related may either be definitely unrelated or simply unlikely to be related (i.e., there are other more likely causes for the AE).

The study sponsor will assess the AEs and may upgrade the investigator's assessment of seriousness and/or causality. The study sponsor will notify the investigator of any AEs that are upgraded from nonserious to serious or from unrelated to related.

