5.3.1 Ocular and Nonocular AEs and SAEs

All adverse events reported to Alcon will be accounted for in the reporting. Descriptive summaries (counts and percentages) and listings will be presented. The type of event (serious, device related, etc.) will be summarized overall and by ocular/non-ocular status. Events will also be summarized by MedDRA preferred term, with the number and percent of subjects and a 95% exact binomial confidence interval, as well as a count of the number of events. The applicable definition of an adverse event is in the study protocol. A listing of all adverse events will be constructed to provide further details.

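### The Related criterion in Protocol 11.3 joins device and procedure, so it does not match the device-only classification that the ADE definition, the safety objective and SAP 5.3.1 require

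*Protocol*

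**What the plan says.** **The causality rule.** Under Protocol 11.3 (Intensity and Causality Assessments), for every AE "the investigator must assess the causality (related or not related to the medical device or study procedure"). Related covers definite relation, and also possible relation where "there is a reasonable possibility that the AE was caused by the medical device or study procedure". The only other category is Not Related. For the second assessor, "An assessment of causality will also be performed by study sponsor utilizing the same definitions". The sponsor notifies the site of events "upgraded from nonserious to serious or from unrelated to related", so the causality change is described on a single scale.

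**What has to come out of it.**
- Protocol 6.4 gives the safety objective: "To obtain device-specific safety clinical data".
- The glossary (Protocol Section 1) defines an ADE as "Adverse event related to the use of an investigational medical device or comparator". The procedure is not named.
- The footnote to Figure 11-1 (Protocol 11.1) says that "only AEs related to the IP/device (i.e., UNITY VCS) are considered as device related ADE".
- SAP 5.3.1 plans that "The type of event (serious, device related, etc.) will be summarized overall and by ocular/non-ocular status". It does not define device related, and it does not say whether the investigator's or the sponsor's assessment is used.

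**The concern.** The only written criterion for Related is wider than the class of events that the study has to report. Every treated subject has intraocular surgery. The SAE list in Protocol 11.1 includes events such as iatrogenic retinal tear, sclerotomy site leakage and posterior capsular tear, which can come from the operation while the system works as designed. Under the wording of 11.3, such an event is Related whenever the procedure is a reasonable cause.

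If that answer supplies the device-related rows of the AE table, those rows absorb procedure-only events and overstate device harm. If something else supplies them, the documents do not say what. The study has a single arm, so no control group shows the background risk of the procedure. Attribution event by event is the only internal means of separating device from procedure, and its criterion should be explicit.

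**Working it through.** The plan gives no figure for this point, so there is none to reproduce. The check is a comparison of texts, followed by an illustration of size.

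**Step 1: compare the criteria.**

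| Place | What counts |
|---|---|
| Protocol 11.3, instruction to investigator | device or procedure |
| Protocol 11.3, definition of Related | device or procedure |
| Protocol 11.3, sponsor assessment | same definitions, so device or procedure |
| Protocol Section 1, ADE | use of the device |
| Protocol 11.1, Figure 11-1 footnote | UNITY VCS only |
| Protocol 6.4, objective | device-specific |
| SAP 5.3.1, event-type summary | device related, undefined |

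The first three rows are wider than the last four. The sponsor's review cannot supply the distinction, because it works from the same definition.

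**Step 2: look for a rule elsewhere that separates device from procedure.** Protocol 11.1 classifies AEs linked to gas, silicone oil and other devices used alongside UNITY VCS separately. It also removes expected femtosecond-laser complications and additional medical interventions from the device-related class. It does not do the same for the vitreoretinal or cataract procedure itself. Protocol 11.3 sends ADEs to a combined SAE/ADE eCRF, so a device-only call is expected, but no criterion for it is given. Nothing in SAP 5.3.1 links its device-related rows to a field or an assessor.

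**Step 3: size, with assumed counts.** The inputs are n = 100 eyes, from the planned 100 surgeries (Protocol 12.8 and SAP 7), and 20 eyes with an AE that meets the joint criterion. The 20 is an assumption and is not in the documents. The number of these that are device related, x, is varied.

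Exact (Clopper-Pearson) 95% limits: lower = Beta quantile 0.025 with parameters (x, n − x + 1), and upper = Beta quantile 0.975 with parameters (x + 1, n − x). The lower limit is 0 when x = 0.

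| Device-related eyes, x | Rate | Exact 95% CI |
|---|---|---|
| 0 | 0% | 0 to 3.6 |
| 2 | 2% | 0.2 to 7.0 |
| 3 | 3% | 0.6 to 8.5 |
| 5 | 5% | 1.6 to 11.3 |
| 10 | 10% | 4.9 to 17.6 |
| 20 (joint criterion) | 20% | 12.7 to 29.2 |

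If only a joint answer were recorded, the device-related rate could lie anywhere from 0 to 20% in this example. With x = 3, the joint criterion reports 20% where the device-only rate is 3%, a gap of 20 − 3 = 17 percentage points.

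**The case against.** A reader might infer that causality is captured in one field, that the answer can never be split, and so that no device-specific rate can be obtained. The case against that reading is strong.

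- **Forms.** The phrase in 11.3 can be read as two questions, one about the device and one about the procedure. The eCRF and the manual of procedures are not among the documents, and Figure 11-1 is not shown. Two fields may already exist.
- **Intent.** The ADE definition, the Figure 11-1 footnote, the separate-classification rules in 11.1 and the ADE reporting form all require a device-only call. Related, with ADE as a subset, could be a deliberate hierarchy.
- **Malfunctions.** A fault in the system goes through the device-deficiency route. It is categorised with any harm reported separately (Protocol 11.1), documented within 24 hours (11.3), and tabulated and listed (SAP 5.3.2). A tear from a fluidics fault would therefore not look the same in the data as one from surgical technique.
- **Reporting time.** Iatrogenic retinal tear and sclerotomy site leakage are SAEs by rule and are due within 24 hours whatever their cause. The device-only call affects that deadline only for nonserious events.
- **Sponsor re-sorting.** A reader might also expect the sponsor to move events out of the device class afterwards. Protocol 11.3 describes upgrades only, so this is not supported.

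All of this stands against the stronger reading. It does not remove the mismatch. Intent to classify by device is not a criterion for doing so, and none of these sections says how device is told from surgical procedure. The device-deficiency route is no substitute, because Protocol 11.1 itself states that an ADE need not stem from a deficiency. If two fields do exist, the written definition of Related is still joint and SAP 5.3.1 still does not name its source.

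**Conclusion.** The point holds as a mismatch between Protocol 11.3 and the places that need device-only events: the glossary, the Figure 11-1 footnote, Protocol 6.4 and SAP 5.3.1. Read literally, procedure-only events meet Related. The documents do not say how device-related events are separated, or whose assessment feeds the SAP summary. They do not show that a device-specific rate is impossible to derive.

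The size cannot be fixed from the documents. The contrast of 20% with 3% rests on assumed counts, and the true gap depends on the share of procedure-only events, which the plan does not give. The study is descriptive, with no safety hypotheses, and all AEs are listed, so no test or sample size is affected. What is affected is the meaning of the device-related rows, which bear directly on the stated safety objective. That makes a clarification worth making.

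**What to change.** **Protocol 11.3.** Have the investigator and the sponsor each record two yes/no judgements for every AE: (a) related to UNITY VCS, and (b) related to the surgical procedure. Apply the existing Related and Not Related criteria to each. State that only a yes to (a) makes an event an ADE, or a SADE if it is serious.

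**SAP 5.3.1.** Name field (a) as the source of the device-related rows and say which assessor's answer is used. Show events that are procedure related only, meaning (b) yes and (a) no, separately. If intervals are wanted for these rows, add an exact 95% CI explicitly, because the one now planned belongs to the preferred-term summary.

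**Cost.** One extra field per AE, a little more investigator time, a few sentences in the protocol and SAP, and one extra table column. If the eCRF already holds both fields, only text and table changes are needed. Sample size and clinical management do not change.

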#### ***Causality***

Related	An AE classified as related may be either definitely related or possibly related where a direct cause and effect relationship with the medical device or study procedure has not been demonstrated, but there is a reasonable possibility that the AE was caused by the medical device or study procedure.
Not Related	An AE classified as not related may either be definitely unrelated or simply unlikely to be related (i.e., there are other more likely causes for the AE).

The study sponsor will assess the AEs and may upgrade the investigator's assessment of seriousness and/or causality. The study sponsor will notify the investigator of any AEs that are upgraded from nonserious to serious or from unrelated to related.

### **11.4 Return Product Analysis**

Study sponsor representatives and their contact information are provided in the MOP that accompanies this protocol.

Alcon study products associated with device deficiencies and/or product related AEs should be returned and must include the complaint number which will be provided by study sponsor after the case is entered in the study sponsor's Global Product Complaint Management System (GPCMS).

## **11.5 Unmasking of the Study Treatment**

Not applicable; this study is an open label study.

## **11.6 Follow-Up of Subjects with Adverse Events**

The investigator is responsible for adequate and safe medical care of subjects during the study and for ensuring that appropriate medical care and relevant follow-up procedures are maintained after the study.

The investigator should provide the study sponsor with any new safety information (which includes new AEs and changes to previously reported AEs) that may affect the safety evaluation of the device. For AEs that are unresolved/ongoing at time of discontinuation, any additional information received at follow-up should be documented in the eCRFs up to study completion (i.e., database lock). Any additional data received up to 6 months after a subject completed the study should be documented and available upon the study sponsor's request.

All complaints received after this time period will be considered and processed as spontaneous (following the post market vigilance procedures) and should be communicated to the medical device's manufacturer as per local requirements. The investigator should also report complaints on non-Alcon products directly to the manufacturer as per the manufacturer's instructions or local regulatory requirements.

## **11.7 Pregnancy in the Clinical Study**

Pregnancy is not reportable as an AE; however, complications may be reportable and will be decided on a case-by-case basis. An Alcon form will be utilized to capture all pregnancy-related information until birth of the child.

# **12 ANALYSIS PLAN**

## **12.1 Subject Evaluability**

Final subject evaluability must be determined prior to locking the database, based upon the deviations and evaluability plan.

## 12.2 Analysis Sets

All eligible subjects will be screened to determine if they meet all inclusion and no exclusion criteria. Subjects who provide informed consent will be considered enrolled in the study.

### 12.2.1 Full Analysis Set

The primary analysis set for the effectiveness outcomes will be the full analysis set. The full analysis set includes all eyes with successful completion of surgery.

### 12.2.2 Safety Analysis Set

The safety analysis set will include all eyes with attempted use of the UNITY VCS (successful or aborted after contact with the eye) and will be used for the safety outcomes. Attempted use of the UNITY VCS is defined as any time the device makes contact with the eye.

## 12.3 Demographic and Baseline Characteristics

Demographic and baseline characteristics will be summarized for each subject. Counts and percentages will be presented for categorical variables such as sex, age, race, and ethnicity. Count (n), mean, standard deviation, median, minimum, and maximum will be presented for continuous variables such as age.

## 12.4 Effectiveness Analyses

### 12.4.1 Analysis of Primary Effectiveness Endpoint(s)

The primary performance endpoint is the percentage of surgeons reporting 'yes' to the binary question of: *"Did UNITY VCS using vitreoretinal or combined surgical functionality perform per the intended use as defined in protocol Section 5.1?"*

#### 12.4.1.1 Statistical Hypotheses

No hypothesis testing of the primary effectiveness endpoint(s) is planned.

#### 12.4.1.2 Analysis Methods

After each surgery, the surgeon completes a user questionnaire. For subjects in the full analysis set, the rate of 'yes' responses to the question listed above will be presented with a count and percentage and will be accompanied by a two-sided exact binomial 95% confidence interval.

## 12.4.2 Analysis of Secondary Effectiveness Endpoints

The secondary endpoints are:

- Total time in the eye from first entry into eye/first trocar in, to incision closure/last trocar out
- Achievement of anatomical success at 3 months postop, i.e., percent of ‘yes’ responses to the question “Was anatomical success achieved for intended treatment (e.g., macular hole closure, retinal attachment, etc. as applicable for the patient’s condition)?”
- Change in BCDVA at 3 months postop when compared to preop

### 12.4.2.1 Statistical Hypotheses

No hypothesis testing of the secondary effectiveness endpoint(s) is planned.

### 12.4.2.2 Analysis Methods

At the surgical visit, the total time in the eye will be recorded as the time from first entry into eye/first trocar in, to incision closure/last trocar out. The total time in eye will be summarized with the number of observations, mean, standard deviation, median, minimum, and maximum times in minutes. A listing will accompany this summary.

At the end of follow-up for each patient, surgeons will evaluate the success of the surgery. For subjects in the full analysis set, the rate of ‘yes’ responses to the question “was anatomical success achieved for intended treatment (e.g., macular hole closure, retinal attachment, etc. as applicable for the patient’s condition)?” will be presented with a count and percentage and will be accompanied by a two-sided exact binomial 95% confidence interval.

BCDVA will be recorded in Snellen and collected at screening, 1 month, and 3 months. BCDVA will be converted to decimal VA. Observed decimal BCDVA values at each study visit and change from 3 months postoperative visit to screening value for the study eye will be presented descriptively (count, mean, median, standard deviation, minimum, and maximum). A categorical summary of Snellen values (not converted to decimal VA) will be produced and will include counts and percentages for each category at screening, 1 month, and 3 months. A listing will be provided which presents visual acuity results at each visit, including data from 1 day and 1 week visits, where uncorrected data may be recorded per standard of care.

